12.4.1 Relevant AEs

Relevant AEs will be summarized as number and percentage of subjects experiencing the event and number of events reported. The analysis of all relevant AEs recorded in the eCRF will be presented by the following variables for FAS and by subgroup EU label; Prior trastuzumab-based regimen overall and last treatment:

- Any relevant AE
- Any AEs of special interest
 - by interest type: Occurrence of diarrhea, Gastro-intestinal disorder, Pulmonary disorder, Reproductive and developmental disorder, Hepatic disorder, Cardiac disorder, Pancreatitis
- Any SAEs
 - by SAE type: Death, Life threatening, Hospitalization due to AE – initial or prolonged, Congenital diseases/abnormalities, Disability/ incapacity and Other clinically significant conditions
- By Severity: Grade 1, 2, 3, 4 and 5
- By Action taken: None, Treatment dose increased, Treatment dose decreased, Treatment discontinued, Corrective treatment
- By Outcome: Recovered, Recovered with sequelae, Recovering, Not recovered, Death, Unknown
 - By Causal relationship to neratinib treatment: Reasonable possibility, Not reasonable possibility

If number of patients is large enough, the following analyses will be performed :

- Relevant AEs by SOC and PT for each Severity grade
- Relevant AEs by SOC and PT for each Severity grade by subgroup Prior trastuzumab-based regimen subgroup
- Relevant AEs by SOC and PT for each Severity grade, for patients with treatment discontinuation reason “Patient wish”

12.4.2 Occurrence of Diarrhea

The occurrence of diarrhea is an AE of particular interest, thus, the following variables will be summarized as number and percentage of subjects experiencing the event and number of events reported for FAS and by subgroup EU label; Prior trastuzumab-based regimen overall and last

Document: ZZA65950_NEAR_SAP_v2.0

Author: [name]

Version Number: 2.0

Version Date: 22SEP2023

treatment; Concomitant Corrective Antidiarrheal Treatment and Concomitant Prophylaxis Antidiarrheal Treatment (section 8.4):

- Any Occurrence of Diarrhea AE
- Any Occurrence of Diarrhea SAEs
 - by SAE type: Death, Life threatening, Hospitalization due to AE – initial or prolonged, Congenital diseases/abnormalities, Disability/ incapacity and Other clinically significant conditions
- By Severity: Grade 1, 2, 3, 4 and 5
- Occurrence of diarrhea episodes by Severity: Grade 1, 2, 3, 4 and 5
- By Action taken: None, Treatment dose increased, Treatment dose decreased, Treatment discontinued, Corrective treatment
- By Outcome: Recovered, Recovered with sequelae, Recovering, Not recovered, Death, Unknown
- By Causal relationship to neratinib treatment: Reasonable possibility, Not reasonable possibility

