4.10 LIMITATIONS OF THE RESEARCH METHODS

The biggest strength of this study is that it will be able to yield data on the utilization of neratinib and its effectiveness in real-life conditions of use and in the current treatment landscape, and in a more varied profile of patients (for example, those with more advanced disease or with certain comorbidities) than those who were evaluated as part of the pivotal ExteNET trial.

However, an observational and retrospective study comes with its limitations which are as follows:

1. Selection bias: Patients (or their next of kin/legal representative) who refuse to participate may limit the representativeness of the study results. Confounding can occur due to unobservable characteristics of patients. Even though a screening log would be established to record the details of patients who received neratinib as part of the EAP in Europe, irrespective of study inclusion status, it would only record patient demographic characteristics. Investigators will be asked to prospectively enroll consecutive patients who meet the eligibility criteria.
2. Retrospective design: since all data in the study will be extracted from past medical records, investigators will have no control over how the data was recorded and managed prior to the study. Furthermore, this retrospective design implies limited control over the exposure (neratinib treatment), covariates and potential confounders.
3. Attrition bias: Patients lost to follow-up and patients who withdraw their consent will be the main source of attrition bias in this observational study. This can threaten sample representativeness if too many patients are lost to follow-up or if they differ from those who are continuing follow-up. Should the proportion of patients lost to follow-up be non-negligible, the target precision will not be reached. To minimize any risks and potential impact, efforts will be undertaken to collect the data from the lost-to-follow-up patient's most recent visit. Baseline characteristics of patients lost-to-follow-up/withdrawn and those who completed the study may be compared, to evaluate representativeness.
4. Missing data: Depending on physician practices, some data might not be systematically measured or available (such as data on AEs). Missing data can bias the descriptions if it is not completely random. Even in cases where missing data is truly random, a potential impact on the precision of

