7.4 Neratinib Initiation

Data analyzed for the neratinib initiation period will consist of all relevant data collected within +/- 30 days of index date.

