8.4 Examination of Subgroups

The following subgroups are of interest, based on patient characteristics at neratinib initiation (index date) or primary diagnosis of breast cancer. Analyses of primary, secondary, and exploratory outcomes may be performed for some or all these subgroups, subject to pertinence and the number of patients in each subgroup:

- EU label status: Yes, No
 - Yes, defined as, HR+ patients with initiation of Neratinib ≤ 1 year from trastuzumab-based treatment completion in adjuvant setting (EU Label population)
 - No, otherwise
- Pathologic stage (AJCC classification) at primary breast cancer: Stage I, Stage II+III
 - If missing, derived as in 2
- Residual disease after neoadjuvant treatment (pathologic complete response [pCR]): pCR, No pCR

- Risk: Low risk (Stage I or N- or pCR), High risk (Stage II/III or N+ or no pCR)
 - N-, defined as, the electronic case report form (eCRF) nodal status category of NX or N0
 - N+, defined as $N \geq 1$ nodal
- Previous adjuvant or neoadjuvant therapy ⁽²⁾: Neoadjuvant + Post neoadjuvant treatment, Adjuvant only
 - Neoadjuvant + Post neoadjuvant, defined as, at least one neoadjuvant and one adjuvant treatment
 - Adjuvant only, defined as, at least one adjuvant treatment and no neoadjuvant
- Prior trastuzumab-based regimen overall (neoadjuvant or adjuvant): Trastuzumab only, Trastuzumab and Pertuzumab, Trastuzumab emtansine (T-DM1), Other anti HER2
- Prior trastuzumab based regimen the last treatment in adjuvant setting before Neratinib initiation: Trastuzumab only, Trastuzumab and Pertuzumab, Trastuzumab emtansine (T-DM1), Other anti HER2
- Hormone Receptor at Primary Breast Cancer Diagnosis: HR+, HR-
 - HR+, defined as either ER or PR or both are positive
 - HR-, defined as if ER and PR are negative
- Concomitant Corrective Antidiarrheal: Yes, No
- Concomitant Prophylaxis Antidiarrheal: Yes, No
- Initial Dose of Neratinib: <240mg, 240mg, >240mg

Table 2 AJCC staging

Primary tumor (T)	Regional lymph nodes (N)	Distant metastasis (M)	Stage
Tis	N0	M0	0
T1	N0	M0	IA
T0	N1	M0	IB
T1	N1	M0	IB
T0	N1	M0	IIA
T1	N1	M0	IIA
T2	N0	M0	IIA
T2	N1	M0	IIB
T3	N0	M0	IIB
T0	N2	M0	IIIA
T1	N2	M0	IIIA
T2	N2	M0	IIIA
T3	N1	M0	IIIA
T3	N2	M0	IIIA
T4	N0	M0	IIIB
T4	N1	M0	IIIB
T4	N2	M0	IIIB
Any T	N3	M0	IIIC
Any T	Any N	M1	IV

N2 and N3 are not collected in the CRF, this regional lymph node categories will be identified by “ ≥ 4 ” lymph nodes involved.

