12.2 Concomitant Treatments

Concomitant treatments will be analyzed over the whole follow-up period. For each therapy type of concomitant treatment [Endocrine therapy, Prophylaxis antidiarrheal and Corrective antidiarrheal therapy in response to AE (diarrhea)], the following variables will be presented for FAS:

- Number and percentage of patients with at least one treatment of the therapy type. Percentage computed among FAS.
- Number and percentage of patients by treatment name. Percentage computed among FAS patients with at least one treatment of the concomitant therapy type.
- Duration of treatment (months)*, calculated as:
 - For discontinued treatments, $(End\ date - Start\ date + 1) / 30.4$
 - For ongoing treatments, $(EOB\ date - Start\ date + 1) / 30.4$

*A patient can contribute with multiple treatments for the same therapy type, the duration of treatment will correspond to the total exposure of the patient to the treatment type.

Note: Other specified treatment names will be coded with WHO Drug version B3 March 2021, the reported and coded terms will be presented in a listing.

For concomitant treatment of Corrective therapy in response to other relevant AE, the following variables will be presented:

- Number and percentage of patients with at least one treatment. Percentage computed among FAS.
- Number and percentage of patients by adverse event description. Percentage computed among FAS patients with at least one corrective therapy in response to other relevant AE.
- Number and percentage of patients by treatment name, as ATC 5th level coded with WHO Drug. Percentage computed among FAS patients with at least one corrective therapy in response to other relevant AE.
- Number and percentage of patients with at least one maximum dosage received. Percentage computed among FAS patients with at least one corrective therapy in response to other relevant AE.
- Duration of treatment (days), calculated as:
 - For discontinued treatments, $(End\ date - Start\ date + 1)$

- For ongoing treatments, (*EOB date - Start date + 1*)

*A patient can contribute with multiple treatments; the duration of treatment will correspond to the total exposure of the patient to the treatment type.

Note: For corrective therapy in response to other relevant AE, the dose, dose unit and frequency, are also collected in the CRF. These details will be presented in a listing.

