12.4 Adverse Events

In this study relevant AEs that occurred between index date and 30 days after Neratinib discontinuation, study entry date or death, whichever occurs first, are collected in the eCRF and will be analyzed. Relevant AEs are defined as all SAEs, AEs leading to dose adaptation or treatment discontinuation, and AEs of interest.

The following are AEs of interest:

- Occurrence of diarrhea
- Gastro-intestinal disorder
- Hepatic disorders
- Cardiac disorders
- Pulmonary disorders
- Pancreatitis
- Reproductive and developmental disorders

SAEs will be identified as those reported as “Serious” on the Adverse Events page of the eCRF, AEs leading to treatment dose change (increase/decrease) or permanent discontinuation of neratinib will be identified from the action taken in the AE details page of the eCRF.

Adverse Events (AEs) will be coded using MedDRA version 24.1.

See Appendix 1 for handling of partial dates for AEs.

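### The diarrhea tables are split by corrective antidiarrheal use, a subgroup that diarrhea itself defines; the prophylaxis subgroup has no window attached to it

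*SAP*

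**What the plan says.** **Corrective use.** SAP 12.4.2 summarizes diarrhea as "number and percentage of subjects experiencing the event and number of events reported", starting with any diarrhea AE, then seriousness, grade, action taken, outcome and causality. This is done for the FAS and by several subgroups, the last two being "Concomitant Corrective Antidiarrheal Treatment and Concomitant Prophylaxis Antidiarrheal Treatment (section 8.4". SAP 12.2 names the corrective type as "Corrective antidiarrheal therapy in response to AE (diarrhea".

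**Timing of the flags.** SAP 8.4 lists both antidiarrheal flags as Yes/No only. Four other pieces of text bear on timing:

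- The 8.4 lead-in says subgroups are "based on patient characteristics at neratinib initiation (index date) or primary diagnosis of breast cancer". SAP 7.2 defines the index date as the date neratinib was first started through the EAP.
- SAP 7.4 defines the neratinib initiation period as "all relevant data collected within +/- 30 days of index date".
- SAP 12.2, which covers prophylaxis, says "Concomitant treatments will be analyzed over the whole follow-up period".
- SAP 12.4 limits AEs to "relevant AEs that occurred between index date and 30 days after Neratinib discontinuation", or to study entry or death if earlier.

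**Second use of the prophylaxis flag.** SAP 12.1 also plans Kaplan-Meier and reverse Kaplan-Meier analyses of permanent discontinuation by prophylaxis.

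**The concern.** A subgroup comparison of incidence is informative only if membership does not depend on the event being counted. Corrective treatment follows diarrhea, so the first row of the table is largely settled before any data are seen. Nor can such treatment be a characteristic at index or at diagnosis, which is how 8.4 describes its subgroups. SAP 12.4.2 singles diarrhea out as an AE of particular interest, so a large Yes/No contrast could be misread as a difference in risk or as an effect of treatment.

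The prophylaxis flag raises a different issue. If patients who begin prophylaxis after index are coded Yes from day 0, they carry immortal time into the discontinuation curve, because they had to be on neratinib still when prophylaxis began. The diarrhea table could likewise count episodes that came before prophylaxis.

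**Working it through.** The documents give no rate for these tables, so there is no planned figure to reproduce. Every rate below is assumed.

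**(a) Corrective split.** Let p be the proportion of patients with diarrhea and c the share of those given corrective treatment.

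- Yes group: a fraction pc of all patients, all with diarrhea, so 100%.
- No group: a fraction 1-pc of all patients, of whom p-pc had diarrhea, so the rate is p(1-c)/(1-pc).

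| p | c = 50% | c = 70% | c = 90% |
|---|---|---|---|
| 60% | 43% | 31% | 13% |
| 70% | 54% | 41% | 19% |
| 90% | 82% | 73% | 47% |

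For example, p = 70% and c = 70% give 0.21/0.51 = 41%. The No rate moves with both p and c, and one cannot be separated from the other.

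A Yes rate below 100% would not show lower risk. It would reflect the shorter AE window in 12.4 compared with 12.2, or incomplete AE records; Protocol 4.10 warns that "some data might not be systematically measured or available (such as data on AEs".

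*Other rows.* SAP 12.4.2 does not state the denominator for grade, action and outcome. If it is all patients, take p = c = 70% with 30% of diarrhea at grade 3 or above regardless of treatment. Grade 3+ then shows as 30% in Yes and 0.7 × 0.3 × 0.3 / 0.51 = 12% in No. Among patients with diarrhea it is 30% in both.

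**(b) Prophylaxis and the discontinuation curve.** Assume no true effect. Let b be the share on prophylaxis at index, S(t) the share still on neratinib at t months, and S = S(12). Late starts occur at a constant rate λ, so that a share r = 1 - exp(-λw) of the rest would start within w months if all stayed on neratinib. The share of the rest who actually start is q, the integral of λ·exp(-λt)·S(t) from 0 to w. Coding every starter Yes from day 0 gives, at 12 months:

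- Yes: S × (b + (1-b)r) / (b + (1-b)q)
- No: S × (1-r) / (1-q)

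Worked case: b = 0.5, S = 0.7 with exponential stopping, r = 0.2, w = 12. Then q = 0.169. Yes is 0.7 × 0.6/0.585 = 71.8%, No is 0.7 × 0.8/0.831 = 67.4%, and the spurious gap is 4.4 points.

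The ranges below use b = 0.5, 30% or 40% stopped by 12 months, and Weibull shape 0.6 or 1.0:

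| Late starts among the rest | Starts within month 1 | Starts over 12 months |
|---|---|---|
| 10% | 0.2 to 0.8 points | 2.2 to 3.2 points |
| 20-40% | 0.4 to 3.6 points | 4.4 to 13.3 points |

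Classified at the index date, q = r = 0 and the gap is 0. For scale, the 95% half-width for 60 v 60 patients at 65% is 1.96 × √(0.65 × 0.35 × 2/60) = 17 points. (SAP 4.2 now expects 120 patients.)

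**(b) Prophylaxis and the diarrhea table.** Null simulation with 80% diarrhea, 40% on prophylaxis at index, and a 10% to 30% chance of a later start among the rest (for late starts after a first episode, among those of the rest who have diarrhea):

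| Late starts occur | Yes v No, 30-day window | Yes v No, 365-day window |
|---|---|---|
| After a first episode | 80.9 v 79.3 to 82.6 v 77.8 | 82.1 v 78.2 to 85.3 v 73.6 |
| While event-free | 79.9 v 80.1 to 79.8 v 80.2 | 77.9 v 81.5 to 74.1 v 84.8 |

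The direction reverses between the two cases.

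**The case against.** **On the corrective split.** The study is descriptive, 12.4.2 plans no test, 8.4 makes subgroup analyses optional, and a Yes column near 100% shows its own circularity. There is already a corrective-treatment row under action taken. This limits the consequence. It does not rescue the split, which 12.4.2 names explicitly and whose first row carries no information. A reader might go further and infer that the grade and outcome rows are certainly distorted. The documents do not support that: the denominator is unstated, and the TLF shells, which set format and content, are not available here.

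**On prophylaxis.** A reader might infer that any reading of the SAP lets later starters into the Yes group, or that the discontinuation curve will be off by up to 13 points. Neither follows. The 8.4 lead-in mentions the index date explicitly. Taken literally it classifies patients on that date, and there is then no bias. SAP 8.4 does not cite the window in 7.4, and the rule in 12.2 is written for the concomitant-treatment tables. The largest gaps need whole-follow-up coding and 20-40% late starts, a rate found nowhere in the documents. Recording reactive treatment separately as corrective should also keep most starts after a first episode out of the prophylaxis group. What stands is that no window is attached to the flag and that the general text can be coded in more than one way, with different results.

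**Conclusion.** The corrective split of diarrhea incidence is uninformative as written. This follows from the SAP's own definitions and needs no assumed rate; the rates only show how far the No figure can wander (13% to 82% over p of 60-90% and c of 50-90%).

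The prophylaxis point is a secondary ambiguity. The bias in the discontinuation curve is nil under the index-date reading. Under the 30-day reading it is below about 1 point with 10% late starts and at most about 3.6 with 20-40%. It reaches several points or more only under whole-follow-up coding. Most of these gaps are well inside sampling error, but a confidence interval would not reflect them. In the diarrhea table even the sign is unknown.

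The primary outcome is unaffected. Severity is minor, and the shells may already settle the denominator or the window.

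**What to change.** **SAP 12.4.2.** Remove the corrective split from the incidence rows and from any row with an all-patient denominator. Show grade, action taken and outcome by corrective use only among patients with at least one diarrhea AE. List patients with corrective treatment but no diarrhea AE as a data check.

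**SAP 8.4.** State that, for analysis, prophylaxis is Yes only if its recorded start is on or before the index date and it had not ended before that date. Later starters count as No. Report how many patients' order rests on an imputed or missing date, since Appendix 1 moves a start with a missing day to the first of the month and leaves a date unimputed when day and month are both missing. State that confounding by indication remains.

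**Cost.** SAP wording and one derivation from dates already collected. Compared with whole-follow-up coding, the prophylaxis group shrinks. With 50% on prophylaxis at index, the loss is about 7-9% if 10% of the rest start later and 13-28% if 20-40% do. With 30% at index and 20-40% late starts it is 26-48%. Those patients still appear in the 12.2 tables.

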13 EXPLORATORY OUTCOMES

The exploratory outcomes described in this section will be analysed for HRAS.

13.1 First Recurrence

The patterns of the first recurrence after neratinib initiation will be described based on frequencies and percentages of the following variables for HRAS by EU label and for FAS by Hormone receptor (section 8.4):

- Number and percentage of patients with a first recurrence. Percentage computed among HRAS.
- Number and percentage of patients by type of the recurrence: Invasive ipsilateral breast tumor recurrence (IIBTR), Invasive contralateral breast cancer recurrence (ICBCR), Regional invasive recurrence (RIR), Distant tumor recurrence (DTR) – or metastasis, Second breast cancer.
Percentage computed among HRAS.
 - Number and percentage of patients by site of recurrence. Percentage computed among HRAS with the type of recurrence:
 - IIBTR, ICBCR and RIR: Breast, Chest, Axillary lymph node(s), Skin, Nipple complex, Other
 - DTR or metastasis: Bone, Skin, Non-regional lymph node(s), Lung, Liver, CNS, Pleura, Adrenal glands, Ovary(ies), Left breast, Right breast, Other
 - If second breast cancer, the type: HR+, Triple negative, Other
- Number and percentage of patients with treatment administered for first recurrence
- Number of treatments by patient
- Treatment name: Trastuzumab, Pertuzumab, T-DM1, T-deruxtecan, Lapatinib, Tucatinib, Other
- Treatment duration (months), calculated as:
 - For discontinued treatment, $(End\ date - Start\ date + 1) / 30.4$
 - For ongoing treatment, $(EOB\ date - Start\ date + 1)$

13.2 Time to Event Analysis

All time to event outcomes described in the subsections below will be summarized using the Kaplan-Meier method as described in section 8.2, for FAS and by subgroup EU label; Previous adjuvant or neoadjuvant therapy; Residual disease after neoadjuvant treatment; Prior trastuzumab-based regimen overall; and Prior trastuzumab-based regimen last treatment. (section 8.4)

Patients for whom the event did not occur or who are lost to follow-up, will be censored at the last recorded date that the patient is known to be alive. For patients alive at end of study will be considered the date of study entry, for patients who withdraw consent will be considered the date of consent withdrawal, for patients lost to follow-up will be considered the date of last contact, as collected in the eCRF.

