4.3.3 Exploratory outcomes

Effectiveness will be evaluated only on HR+ patients based on the following outcomes, until the end of study observation period:

1. Characterization of first recurrence patterns (location, distribution, size, date)
2. iDFS, defined as the time from neratinib treatment initiation to:
 - a. First ipsilateral invasive breast cancer recurrence
 - b. First regional invasive breast cancer recurrence
 - c. First contralateral invasive breast cancer recurrence
 - d. First distant tumor recurrence
 - e. Death attributable to any cause.
3. DDFS, defined as the time from neratinib treatment initiation to the first distant tumor recurrence or death from any cause.
4. Incidence of CNS metastasis (either isolated or concurrent with other metastatic sites), defined as the time from neratinib initiation to CNS recurrence as first distant recurrence.
5. OS, defined as the time between neratinib treatment initiation (for early breast cancer) and death (due to any cause)

The following key data items will be collected for the **first three** clinical exploratory outcomes:

1. Recurrences after neratinib initiation: date of documented recurrence and site of recurrence, including size and distribution.
 - a. Invasive ipsilateral breast tumor recurrence
 - b. Invasive contralateral breast cancer
 - c. Local/regional invasive recurrence
 - d. Appearance / Occurrence of metastasis /Distant recurrence, including CNS metastasis
2. Date of death and cause of death (related to this cancer, non-breast cancer related, related to another cancer, related to neratinib, other, unknown)
3. Date of last patient visit during follow-up (if applicable)

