4.7 DATA ANALYSIS

4.7.1 General considerations

All statistical analyses will be performed by using statistical analysis system (SAS)[®] version 9.4 or higher (SAS Institute, Cary, NC, USA). A detailed Statistical Analysis Plan (SAP) will be validated by the Sponsor before the database lock. Should there be any major changes in the planned analyses, an amendment to the SAP will be made prior to database lock. Deviations from the SAP after database lock will be outlined in the clinical study report and/or statistical analysis report.

Study outcomes will be analyzed for the full analysis set (comprising of all patients enrolled in the study), and also by country and other predefined subgroups of interest (see section 4.3.4), which will be detailed in the SAP. Where possible, and if allowed by the number of patients, a descriptive analysis of the outcomes across various subgroups will also be performed in an exploratory manner.

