6.3 HR+ Analysis Set [HRAS]

The HR+ analysis set (HRAS) will contain all HR+ patients from the full analysis set, i.e., who had either Estrogen receptor (ER) positive or Progesterone receptor (PR) positive or both positive at primary breast cancer diagnosis.

Document: ZZA65950_NEAR_SAP_v2.0

Author: [name]

Version Number: 2.0

Version Date: 22SEP2023

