7.10 Changes from Protocol

In the eCRF an additional inclusion criterium was considered, i.e., the patient was diagnosed with HER2+ breast cancer. For analysis proposes this additional criterium is considered in the analysis datasets and used in the identification of the FAS.

In the protocol the study entry date was defined as the cut-off date until when the eligible patients' data as obtained from medical charts are abstracted for analysis in the study. Based on a request from Pierre Fabre, the study entry date was assigned in the SAP to the date of first patient in, 05 July 2022, to ensure that all patients have the same cut-off date.

In section 8.2, two additional periods were considered in the time to event analysis, i.e., in protocol the intervals considered were 1, 3, 6, 9 and 12 and for analysis the periods that will be considered are 1, 3, 6, 9, 12, 15 and 18.

The subgroup analysis considered in section 8.4 has been updated from protocol. The nodal status at initial diagnosis and the tumor size at initial diagnosis were removed from the subgroups of interest. The subgroup previous adjuvant or neoadjuvant therapy was defined in the protocol as "Yes/ No" and will be updated to "Neoadjuvant + Post neoadjuvant treatment/ Adjuvant only".

The following subgroups analysis was added: according to EU label status, Concomitant Corrective Antidiarrheal, Concomitant Prophylaxis Antidiarrheal, Initial Dose of Neratinib.

In the protocol the exploratory analysis was planned to be performed only in HR+ patients, it will be analyzed separately for HR+ / HR- patients.

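### SAP 13.2 puts the iDFS, DDFS, CNS metastasis and OS curves on the pooled FAS with no hormone-receptor split, and 13.1 gives no valid denominator for HR- patients

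*SAP*

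**What the plan says.** The documents describe the population for the exploratory outcomes in several places.

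- **Protocol 4.3.3:** "Effectiveness will be evaluated only on HR+ patients". The objectives for iDFS, DDFS and OS (Protocol 3.3, SAP 3.3) are worded for HR+ patients; the CNS metastasis objective carries no such limit.
- **Protocol 4.7.1** gives a general rule: "Study outcomes will be analyzed for the full analysis set (comprising of all patients enrolled in the study".
- **SAP 7.10** records a change from the protocol's HR+ restriction: "it will be analyzed separately for HR+ / HR- patients".
- **SAP 6.3:** "The HR+ analysis set (HRAS) will contain all HR+ patients from the full analysis set".
- **SAP 13, lead sentence:** "The exploratory outcomes described in this section will be analysed for HRAS".
- **SAP 13.2** covers all four time-to-event outcomes: "Kaplan-Meier method as described in section 8.2, for FAS and by subgroup EU label". The other factors listed are prior therapy setting, residual disease after neoadjuvant treatment, and prior trastuzumab-based regimen (overall, and last treatment). Sections 13.2.1 to 13.2.4 name no other population.
- **SAP 8.4** lists hormone receptor among the possible subgroups, but as an option: "Analyses of primary, secondary, and exploratory outcomes may be performed for some or all these subgroups".
- **SAP 13.1** presents first recurrence for HRAS by EU label and for FAS by hormone receptor. The overall and by-type percentages are computed among HRAS, and the site percentages among HRAS patients with that type of recurrence.

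**The concern.** There are two separate faults.

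**Population in 13.2.** Section 7.10 replaces an HR+ restriction with a split, and neither of those is pooling. Section 13.2 asks for the pooled set and leaves hormone receptor off its list. A programmer who follows 13.2 alone would produce a FAS curve that mixes HR+ and HR- patients, and no HR- curve. The report could then show a pooled curve beside objectives written for HR+ patients, with nothing in the plan to say which curve is the main one. These are the study's only survival results, so the choice should not be left until results are known.

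**Denominators in 13.1.** The hormone-receptor table needs an HR- column, but every stated denominator is a set that excludes HR- patients. Taken strictly, the HR- percentage cannot be computed. If HR- counts are simply put over HRAS, it is computed on the wrong group.

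**Working it through.** **1. Populations side by side**

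| Place | Population for the time-to-event outcomes |
|---|---|
| Protocol 4.3.3 | HR+ only |
| SAP 7.10 | HR+ and HR-, separately |
| SAP 13, lead sentence | HRAS (HR+ only) |
| SAP 13.2 | FAS, by five factors without hormone receptor |
| SAP 8.4 | hormone receptor split optional |

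HRAS is the HR+ half of the 7.10 split, so the lead sentence fits 7.10 but is incomplete. Section 13.2 contains neither half.

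**2. Does EU label stand in for the split?** No. SAP 8.4 has "Yes, defined as, HR+ patients with initiation of Neratinib" within one year of completing adjuvant trastuzumab-based treatment, so the Yes level is only part of HRAS. The No level is everyone else, which mixes HR- patients with HR+ patients who started later.

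**3. Size of pooling.** The plan gives no figure to reproduce. The shift (FAS minus HRAS) is

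HR- share × (S for HR- minus S for HR+).

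Assumptions, since the documents give neither the HR mix nor HR- survival:
- HR- share 0 to 30%.
- 24-month HR+ iDFS 93.9%. This is the neratinib-arm figure for the whole pivotal trial in Protocol 2, used as a stand-in.
- 24-month HR- iDFS 85 to 97%.
- Constant hazard, so S(18) = S(24)^0.75. Eighteen months is the last tabulated time in SAP 8.2.

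At 18 months:
- HR+: 0.939^0.75 = 0.954
- HR-, low: 0.85^0.75 = 0.885; shift 0.30 × (0.885 - 0.954) = -2.1 points
- HR-, high: 0.97^0.75 = 0.977; shift 0.30 × (0.977 - 0.954) = +0.7 points
- Share 0: shift 0

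**4. Denominators in 13.1.** If HR- counts are divided by HRAS, the overall and by-type percentages print at n(HR-)/n(HR+) of their true value:
- 5% share: 0.05/0.95 = 0.05
- 30% share: 0.30/0.70 = 0.43

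Example with the 120 patients of SAP 4.2 and an assumed 30% HR- share (36 HR-, 84 HR+): 4 recurrences in HR- patients are 4/36 = 11.1%, but print as 4/84 = 4.8%.

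For site percentages the ratio is share × RR/(1 - share), where RR is the HR- to HR+ risk ratio for that type of recurrence. At a 30% share and RR = 2 it is 0.30 × 2/0.70 = 0.86. It passes 1 only when RR exceeds 0.70/0.30 = 2.33.

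**5. Precision of the separate groups.** Wilson 95% intervals at 18 months, assuming no loss before then. Minimum potential follow-up, from 31 December 2020 to 5 July 2022, is 552/30.4 = 18.2 months. The event-free counts are illustrative.

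| Group | Event-free | 95% CI |
|---|---|---|
| HR-, 30% share | 32/36 | 74.7 to 95.6% |
| HR-, 5% share | 5/6 | 43.6 to 97.0% |
| HRAS, 30% share | 80/84 | 88.4 to 98.1% |
| FAS | 112/120 | 87.4 to 96.6% |

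The FAS row is the sum of 80/84 and 32/36. The HRAS interval is 9.7 points wide and the FAS interval 9.2.

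**The case against.** The strongest reply is that the sections add up instead of conflicting: HRAS from the lead sentence, FAS from 13.2, and HR- from 7.10 with 8.4. Protocol 4.7.1 supplies a general basis for FAS. The TLF shells mentioned in SAP 9 may show the intended layout, but they are not among the documents.

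Much of this stands. A reader might infer that nobody can tell which curve answers the HR+ objectives. The documents do not support that: the iDFS, DDFS and OS objectives are for HR+ patients, HRAS is defined as exactly those patients, and the lead sentence assigns the exploratory outcomes to it. Nor has the SAP dropped the HR- analysis, because 7.10 states it.

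What remains on the additive reading is that 13.2 names no main population, leaves its FAS curve unlabelled and specifies no HR- curve. Section 8.4 only permits one. The neighbouring 13.1 writes the hormone-receptor split out, so its absence from 13.2 is a gap. Protocol 4.7.1 is general, while 4.3.3 is the specific rule for effectiveness.

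On 13.1, HRAS is the right base for the whole-HRAS display. A reader might also infer that HR- percentages will print at 5 to 43% of their true value. That follows only if HR- counts are placed over HRAS; on a strict reading the percentage is undefined. The firm finding is that a denominator is missing.

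Finally, the outcomes are exploratory and descriptive, so no error rate or sample size is affected.

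**Conclusion.** Both faults hold on the text and should be fixed. Section 13.2 is out of line with the Section 13 lead sentence, 7.10 and Protocol 4.3.3, and does not deliver the HR- analysis that 7.10 says will be done. Section 13.1 has no valid denominator for HR- patients; this follows from the definition of HRAS and needs no assumption.

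The numerical effects are less certain. The size and even the sign of the pooling shift cannot be determined from the documents. The range of -2.1 to +0.7 points at 18 months rests wholly on the assumed HR- share, the assumed HR- iDFS, the whole-trial stand-in for HR+ patients and a constant hazard; it is zero if every patient is HR+. The 4.8% against 11.1% example rests on an assumed 30% HR- share and one way of programming the table. Confidence is high in the mismatch of wording and much lower in its size.

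**What to change.** Change SAP text only:

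- **13.2:** name HRAS as the main population for iDFS, DDFS and OS. Add the hormone-receptor split so that HR- patients are shown separately, and label any pooled FAS curve supplementary.
- **CNS metastasis:** apply the same HR+/HR- split, on the basis of Protocol 4.3.3 and SAP 7.10, and note that its objective has no HR+ restriction.
- **Section 13 lead sentence:** align it with 7.10, since it now mentions HRAS alone.
- **13.1:** compute overall and by-type percentages within each displayed group, and site percentages within that group's patients who had that type of recurrence.

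The cost is wording and matching table labels. Receptor status is already collected and HRAS already defined, so no new data or protocol change is needed. The downside is precision. At 120 enrolled, an assumed HR- share of 5 to 30% means 6 to 36 patients and wide HR- intervals, and the HRAS curve is slightly less precise than the FAS curve, as the intervals above show.
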